Study aim	
The study aims to establish an Italian registry for the implementation of the use of genomic tests in patients with HR+/HER2- breast cancer at intermediate risk of recurrence after the entry into force of the Ministerial Decree of 18/05/2021. The decree has established the reimbursability of genomic testing for breast cancer patients, thereby influencing clinical decision-making and patient management within Breast Units.
 
In addition, the study aims to evaluate the clinical impact of the use of genomic testing on the type of adjuvant treatment, in terms of change of treatment indication by breast units according to the test result.
 
The retrospective cohort will contribute to expanding our knowledge of the clinico-pathological characteristics of patients who underwent genomic testing. This comprehensive understanding of the clinico-pathological profile of patients undergoing genomic testing will enable a more thorough assessment of the clinical dynamics and therapeutic decisions associated with genomic testing results, including the analysis of their possible evolution over the years.

Study Design	
The study is a retrospective and prospective, non-interventional, observational registry-based study that will enroll all patients with ER+/HER2-negative, T1-3 breast cancer with negative axillary lymph nodes or up to 3 positive axillary lymph nodes for whom Breast Units require genomic test to support adjuvant therapy decisions, according to current clinical practice.
 
For prospective cohort: genomic tests will be performed on all patients who meet the criteria for access to testing as set out in the Ministerial Decree of 18/05/2021, unless otherwise agreed by the reference Breast Unit, in accordance with the specific diagnostic pathways activated by each site.
 
For retrospective cohort: data for patient referred for genomic testing following Ministerial Decree 18/05/2021 will be collected.
 
The patient's baseline demographic characteristics, tumor clinicopathological features, pre and post-test therapeutic indication (CET vs ET), the test results, the actual adjuvant treatment received and time around data will be recorded in a dedicated registry.

Duration of the study	18 months
Primary endpoints	1. Establishment of a prospective Italian observational registry for the implementation of genomic tests in patients with HR+/HER2- breast cancer at

	
intermediate risk of recurrence after the adoption of the Ministerial Decree of 18/05/2021
 
2. Measurement of the impact of genomic testing on adjuvant treatment choice (CET vs ET only) in terms of:
 
- Rate of adjuvant treatment choice's change following the genomic test result (Breast Unit's pre-test vs post-test indication)- Saving in adjuvant chemotherapy compared to the pre-test indication- Addition of adjuvant chemotherapy to endocrine therapy alone compared to the pre-test indication- Type of adjuvant treatment the patient actually received
Secondary Endpoints	
- Record the predominant demographic and clinical characteristics of the patients for whom genomic testing was indicated.- Describe which genomic tests are used and the factors involved in the selection of genomic tests.- Identify any inequalities in access to the genomic tests in different geographical areas of the country.- Analyse the prescriptive adequacy and the compliance with the inclusion criteria for genomic tests.- Record the distribution of demographic and clinical characteristics (e.g., patient age, comorbidities, tumour size, number of positive lymph nodes, tumour grade) in the group of patients with changed treatment recommendation compared to the group of patients with unchanged indication after genomic test.- Evaluate the impact of the test on the timing of activation of adjuvant treatment, in terms of:
o Time from diagnosis to request for genomic testo Time from request for the genomic test to resulto Time from test result to activation of adjuvant chemotherapy, if indicatedo Time from diagnosis to activation of adjuvant chemotherapy, if indicated
Patients number	1.000 patients
Study Population	
Inclusion Criteria
 
All male and female patients meeting these criteria:
 
1. Age \geq 18 years2. PS ECOG 0-13. Histologically confirmed early breast carcinoma with positivity for hormone receptors (ER+ IHC $>10\%$) and HER2 negative (IHC value 0-1+ and/or FISH not-amplified)4. Primary resective surgery for early breast cancer with adequate assessment of lymph node status (sentinel lymph node biopsy or complete axillary dissection), with one of the following diagnostic stages:
• T1-3, N0, M0• T1-3, pN1mic, M0• T1-3, pN1a, M0

	
5. Indication for adjuvant treatment with endocrine therapy (ET) or chemo-endocrine therapy (CET), according to the decision of the reference Breast Unit6. Meeting the criteria for "intermediate" risk, i.e., no "low" or "high" risk of recurrence, as defined in the ministerial decree of 18/05/21:
• Low risk defined by at least 5 of the following: G1, T1a-b, Ki67 < 15, N neg, ER > 80%• High risk, defined by at least 4 of the following: G3, T > 2, Ki67 > 30, N pos, ER < 30%7. Indication for genomic test (Oncotype DX®, Mammaprint®, PAM50-Prosigna®, Breast Cancer Index®, EndoPredict®) by the Breast Unit8. Ability to provide written informed consent to participate in the registry study, approved by the local Ethics Committee.9. The patient underwent genomic testing starting from September 2021
	
Exclusion criteria
 
1. Low-risk and High-risk patients as defined in the Ministerial Decree of 18/05/212. ER negative and/or HER2 positive tumours3. More than 3 lymph nodes involved at clinical/pathological staging4. Invasive tumours <2mm evaluated by local pathologists5. Previous history of breast cancer6. Synchronous breast cancers7. Multifocal tumours8. Metastatic disease9. Contraindications to adjuvant treatments10. Performance status (PS ECOG) > 1 and / or other clinical factors that would make the patient a candidate and unsuitable for systemic adjuvant treatment or have received an exclusive indication for precautionary hormone therapy as part of the Breast Unit collegial assessment.11. Psychiatric diagnosis that may affect the ability to participate in this study
Statistical methods	Although the true nature of this registry does not define apriori the number of patients ultimately expected, one of the main factors driving the sample size of this study is the clinical impact analysis and focuses on the accuracy of the estimate of the proportion of changes in planned adjuvant therapy pre and post genomic results.
Study Duration	Duration of the Project: 18 months Ethics committee submission: June 2023 Patient enrolment: May 2024-May 2025 End of Follow-up: November 2026

1 BACKGROUND AND INTRODUCTION

Breast cancer (BC) is the most common cancer in women, with approximately 55,000 new diagnosed cases per year in Italy and 13,000 BC specific deaths. After BC surgery, adjuvant treatment with radiotherapy, endocrine therapy and chemotherapy in selected cases, represents the standard of care for hormone-positive (HR +), HER2-negative early breast cancer (eBC).

The choice of the type of adjuvant treatment generally takes into account the clinicopathological characteristics of the patient and the tumour, including age, menopausal status, tumour size, grading and Ki67 labelling index, number of lymph nodes involved and hormone receptor expression. These characteristics configure specific and different BC risk profiles and drive the individual adjuvant BC treatment as for recommended international guidelines.

However, some ambiguity still remains in the optimal adjuvant treatment in HR+/HER2- eBC, particularly regarding whether patients should receive or not adjuvant chemotherapy (CT) in addition to endocrine treatment (ET). Considering the absolute clinical benefit of adjuvant CT in addition to ET in HR + eBC with negative lymph nodes (N0) is modest (4% absolute recurrence risk reduction at 10 years), and considering that currently about 50% of patients with HR+/HER2- eBC still receive adjuvant CT, the proper patient selection for CT is a major clinical unmet need. The same applies to older patients (post-menopausal) with HR +/HER2- eBC with limited lymph node involvement (N1a), for whom the use of adjuvant CT is often associated with increase toxicity and avoidable side-effects.

Consequently, there is an urgent clinical need to support the optimal decision-making process for determining the best postoperative therapy, especially for "intermediate" risk patients for whom it is unclear whether they should receive endocrine therapy alone (ET) or chemotherapy (CT).

In recent years, the role of molecular classifiers in prognosis and prediction has increased considerably. Indeed, several tests have been developed that assess the expression of panels of genes involved in the cellular replication of tumour cells and their metastatic ability, revealing specific genomic profiles associated with different risk of recurrence. Eventually, these tools can be used to refine the individual patients' prognosis and to estimate the benefit expected of adjuvant treatment. Accordingly, these tests provide critical support for therapeutic choice in patients with HR +/HER2- eBC (stage I-IIIA) at intermediate risk of recurrence according to clinical and histopathological factors, and help define whether adjuvant chemotherapy is appropriate in addition to endocrine therapy alone.

Several clinical trials have investigated the impact of these molecular classifiers on the choice of therapy. Multigenic tests have significantly changed the choice of treatment in a substantial proportion of patients, largely sparing the need for additional chemotherapy in favour of endocrine therapy alone.

Currently, some of these classifiers are available for routine clinical use in Italy, including OncotypeDX, Endopredict, Prosigna and Mammaprint. In line with the growing scientific evidence, the Ministry of Health, by decree of 18 May 2021, recognised the utility of genomic breast genomic tests and established their reimbursement according to some clinical criteria that can define the intermediate risk of recurrence, as derived from the scientific literature and the results of 3 prospective Italian experiences with the use of OncotypeDX.

The Ministry estimates that approximately 10,000 patients per year are expected to have access to the tests, resulting in a potential saving in chemotherapy prescription > 50% compared to what is currently proposed. Conversely, it is estimated that in about 10% of patients eligible for adjuvant endocrine therapy alone, the genomic test result will change the therapeutic approach and indicate the need to associate chemotherapy.

2 RATIONALE

With the receipt of the ministerial decree, Italian Breast Units have made genomic tests available to patients according to national indications, although availability varies from region to region. Irrespective of the estimates of the expected use of genomic tests, it is crucial to assess the actual degree of implementation of the use of genomic tests in accordance with ministerial indications, their prescriptive suitability and, finally, the clinical-therapeutic impact since the decree came into force.

Understanding the clinico-pathological characteristics of patients undergoing genomic tests is crucial for personalized cancer care. This understanding enables clinicians to tailor treatment plans effectively by identifying specific patient characteristics that correlate with certain genomic profiles. This approach improves treatment outcomes and reduces adverse effects. Additionally, integrating clinico-pathological characteristics with genomic data enhances prognostication, providing patients with more accurate prognostic information and enabling better long-term management strategies.

Furthermore, this comprehensive understanding facilitates the identification of predictive biomarkers, guiding the selection of effective therapeutic interventions and driving the development of innovative targeted therapies. By assessing the evolution of clinico-pathological characteristics and treatment decisions over time, the study provides insights into the long-term effectiveness of genomic testing, allowing for continuous quality improvement and optimization of treatment protocols.

Ultimately, findings from this study inform the development of clinical practice guidelines and health policies, guiding evidence-based decisions on resource allocation, reimbursement policies, and the integration of genomic testing into standard clinical practice. This comprehensive approach to understanding clinico-pathological characteristics in patients undergoing genomic testing contributes to the delivery of more effective, personalized cancer care, thereby improving patient outcomes and quality of life.

3 OBJECTIVES OF THE STUDY

The study aims to establish an Italian registry for the implementation of the use of genomic tests in patients with HR +/HER2- breast cancer at intermediate risk of recurrence after the entry into force of the Ministerial Decree of 18/05/2021. The decree has established the reimbursability of genomic testing for breast cancer patients, thereby influencing clinical decision-making and patient management within Breast Units.

In addition, the study aims to evaluate the clinical impact of the use of genomic testing on the type of adjuvant treatment, in terms of change of treatment indication by breast units according to the test result.

The retrospective cohort will contribute to expanding our knowledge of the clinico-pathological characteristics of patients who underwent genomic testing. This comprehensive understanding of the clinico-pathological profile of patients undergoing genomic testing will enable a more thorough assessment of the clinical dynamics and therapeutic decisions associated with genomic testing results, including the analysis of their possible evolution over the years.

4 ENDPOINTS

4.1 Co-primary endpoints

1. Establishment of a prospective Italian observational registry for the implementation of genomic tests in patients with HR +/HER2- breast cancer at intermediate risk of recurrence after the adoption of the Ministerial Decree of 18/05/2021
2. Measurement of the impact of genomic testing on adjuvant treatment choice (CET vs ET only) in terms of:
 - Rate of adjuvant treatment choice's change following the genomic test result (Breast Unit's pre-test vs post-test indication)
 - Saving in adjuvant chemotherapy compared to the pre-test indication
 - Addition of adjuvant chemotherapy to endocrine therapy alone compared to the pre-test indication
 - Type of adjuvant treatment the patient actually received

4.2 Secondary endpoints

- Record the predominant demographic and clinical characteristics of the patients for whom genomic testing was indicated.
- Describe which genomic tests are used and the factors involved in the selection of genomic tests.
- Identify any inequalities in access to the genomic tests in different geographical areas of the country.
- Analyse the prescriptive adequacy and the compliance with the inclusion criteria for genomic tests.
- Record the distribution of demographic and clinical characteristics (e.g., patient age, comorbidities, tumour size, number of positive lymph nodes, tumour grade) in the group of patients with changed treatment recommendation compared to the group of patients with unchanged indication after genomic test.
- Evaluate the impact of the test on the timing of activation of adjuvant treatment, in terms of:
 - Time from diagnosis to request for genomic test
 - Time from request for the genomic test to result
 - Time from test result to activation of adjuvant chemotherapy, if indicated
 - Time from diagnosis to activation of adjuvant chemotherapy, if indicated

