2. PS ECOG 0-1
3. Histologically confirmed early breast carcinoma with positivity for hormone receptors (ER+ IHC >10%) and HER2 negative (IHC value 0-1+ and/or FISH not-amplified)

4. Primary resective surgery for early breast cancer with adequate assessment of lymph node status (sentinel lymph node biopsy or complete axillary dissection), with one of the following diagnostic stages:
T1-3, N0, M0
T1-3, pN1mic, M0
T1-3, pN1a, M0
5. Indication for adjuvant treatment with endocrine therapy (ET) or chemo-endocrine therapy (CET), according to the decision of the reference Breast Unit
6. Meeting the criteria for "intermediate" risk, i.e., no "low" or "high" risk of recurrence, as defined in the ministerial decree of 18/05/21:
 - Low risk defined by at least 5 of the following: G1, T1a-b, Ki67 < 15, N neg, ER > 80%
 - High risk, defined by at least 4 of the following: G3, T > 2, Ki67 > 30, N pos, ER < 30%
7. Indication for genomic test (Oncotype DX®, Mammaprint®, PAM50-Prosigna®, Breast Cancer Index®, EndoPredict®) by the Breast Unit
8. Ability to provide written informed consent to participate in the registry study, approved by the local Ethics Committee.
9. The patient underwent genomic testing starting from September 2021

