5.2 Exclusion criteria

1. Low-risk and High-risk patients as defined in the Ministerial Decree of 18/05/21
2. ER negative and/or HER2 positive tumours
3. More than 3 lymph nodes involved at clinical/pathological staging
4. Invasive tumours <2mm evaluated by local pathologists
5. Previous history of breast cancer
6. Synchronous breast cancers
7. Multifocal tumours
8. Metastatic disease
9. Contraindications to adjuvant treatments
10. Performance status (PS ECOG) > 1 and / or other clinical factors that would make the patient a candidate and unsuitable for systemic adjuvant treatment or have received an exclusive indication for precautionary hormone therapy as part of the Breast Unit collegial assessment.
11. Psychiatric diagnosis that may affect the ability to participate in this study

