6 STUDY DESIGN

The study is a retrospective and prospective, non-interventional, observational registry-based study that will enrol all patients with ER +/HER2-negative, T1-3 breast cancer with negative axillary lymph nodes or up to 3 positive axillary lymph nodes for whom Breast Units require genomic test to support adjuvant therapy decisions, according to current clinical practice.

Only patients who fulfill certain criteria specified in Ministerial Decree 18/05/2021 will be included unless otherwise agreed by the reference Breast Unit, in accordance with the specific diagnostic pathways activated by each site.

Data will be collected from September 2021 onwards. The tests are conducted as part of routine clinical care, independent of this observational clinical study.

The patient's baseline demographic characteristics, tumour clinicopathological features, pre and post-test therapeutic indication (CET vs ET), the test results, the actual adjuvant treatment received and time around data will be recorded in a dedicated registry.

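### Regional access and prescribing compliance cannot be answered by a registry that enrols only tested, decree-eligible patients, and section 6 contradicts the enrolment criteria

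*Protocol*

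**What the plan says.** Two secondary endpoints in Protocol section 4.2 are at issue: "Identify any inequalities in access to the genomic tests in different geographical areas of the country" and "Analyse the prescriptive adequacy and the compliance with the inclusion criteria for genomic tests". Section 2 gives their purpose. It notes that availability differs between regions and treats real-world implementation and the suitability of prescribing as central questions.

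The enrolment rules are these:

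- Section 5.1, item 7 requires a Breast Unit indication for a genomic test. Item 9 requires that "The patient underwent genomic testing starting from September 2021".
- Section 5.1, item 6 requires intermediate risk, meaning neither low nor high "risk of recurrence, as defined in the ministerial decree of 18/05/21". Section 5.2, item 1 excludes "Low-risk and High-risk patients as defined in the Ministerial Decree of 18/05/21". The synopsis repeats both, and none of these places allows an exception.
- Section 6 says that only patients meeting certain decree criteria "will be included unless otherwise agreed by the reference Breast Unit".
- The synopsis, under Study Design, uses the same qualifier for a different matter, namely who is tested in the prospective cohort. Tests are done on all patients meeting the access criteria "as set out in the Ministerial Decree of 18/05/2021, unless otherwise agreed by the reference Breast Unit".

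On data, section 7.2 lists region of origin, grade, tumour size, nodal status, ER and Ki67 for consenting patients. Section 9 has the platform monitor enrolled numbers with geographic information. Section 6 adds that "the actual adjuvant treatment received and time around data will be recorded in a dedicated registry".

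**The concern.** Inequality of access is mainly about patients who could have been tested and were not. A registry whose entry condition is a completed test contains none of them. The synopsis wording itself foresees that some decree-eligible patients will not be tested. Regional counts of enrolled patients would then largely show which of the roughly 25 sites joined and how much each enrolled.

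Compliance with the decree has the mirror-image problem. If patients outside the intermediate class are barred from entry, nearly everyone enrolled complies, and a high figure could be read as good prescribing when the eligibility criteria produced it. If sites follow section 6 instead, the figure depends on how often each unit admits exceptions, and section 7.2 lists no item recording such an agreement. In that case off-criteria patients also enter the denominator of the co-primary treatment-change endpoint (section 4.1), although section 3 directs the registry at intermediate risk.

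**Working it through.** **The plan's own figures.** The only precision figures are the section 8.2 intervals at n = 1000. The confidence level is not stated there; 95% is assumed (z = 1.96). The Wilson interval is

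[p + z²/2n ± z·√(p(1−p)/n + z²/4n²)] / (1 + z²/n).

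- p = 50%: 46.9% to 53.1%, as stated.
- p = 10%: 8.3% to 12.0%, as stated.
- p = 40%: 37.0% to 43.1%, as stated.

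All three reproduce. They concern treatment change only. The protocol gives no figure for either secondary endpoint, so the rest is a check of what the enrolled data can identify.

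**(a) Access.** Uptake in an area = tested / (tested + eligible untested). Items 7 and 9 of section 5.1 leave the second term of the denominator unobserved. The only population figure, about 10,000 patients a year expected to have access (section 1), is national and has no regional split. Suppose the registry holds 200 tested patients from one area and 100 from another (assumed counts):

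| Eligible in each area (assumed) | Uptake in each area | Ratio |
|---|---|---|
| 250 and 125 | 200/250 = 80%; 100/125 = 80% | 1.00 |
| 250 and 250 | 200/250 = 80%; 100/250 = 40% | 2.00 |
| 400 and 125 | 200/400 = 50%; 100/125 = 80% | 0.625 |

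The registry data are identical in all three rows, so they cannot separate equal access from a disparity in either direction. Differences among tested patients by region remain observable: test type, time from diagnosis to request, and time from request to result.

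**(b) Compliance.** Let p be the true share of tests ordered within the decree risk class. Let f be the admission rate of off-criteria tested patients relative to in-criteria ones. Neither is in the documents.

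Observed compliance = p / (p + f(1 − p)).

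With p = 0.8 (assumed):

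- f = 0 (sections 5.1 and 5.2 applied strictly): 0.8/0.8 = 100%.
- f = 0.5: 0.8/(0.8 + 0.1) = 0.8/0.9 = 88.9%.
- f = 1 (section 6 exception always used): 0.8/(0.8 + 0.2) = 80%.

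At f = 0 the result is 100% whatever p is. The observed figure equals the truth for every p only at f = 1. Under the strict criteria, values below 100% can arise only from patients misclassified at entry.

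**The conflicting rules side by side.** Sections 5.1 and 5.2 and the synopsis criteria bar low-risk and high-risk patients outright. Section 6 makes inclusion subject to a Breast Unit exception. The synopsis Study Design text attaches that exception to testing. The first two cannot both govern enrolment.

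**The case against.** The strongest reply is that section 4.2 promises no rate. It asks to identify inequalities and to analyse compliance, and both can be done descriptively among tested patients. This stands in part: reading uptake or a prescribing rate into the endpoints is an inference from section 2, and it would be wrong to conclude that nothing about access can be studied. An external regional denominator could also be named in an analysis plan that is not shown here. The registry alone still cannot supply one.

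Second, section 6 may be a careless condensation of the synopsis sentence on testing, since both refer to site-specific diagnostic pathways. That is plausible. A reader might infer that off-criteria patients will be enrolled and will bias the co-primary endpoint by some calculable amount. The documents do not support this. Any figure would need an assumed off-criteria share, an assumed admission rate and an assumed difference in change rates. Setting a shift in an overall change rate against the section 8.2 interval for 50% would also compare different quantities, because that interval is for changes from chemotherapy to endocrine therapy alone.

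Third, a reader might infer from the section 7.2 list that the dates needed for timing will not be collected. Section 4.2 defines the intervals and section 6 commits to timing data, so naming the dates is clarification only.

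Fourth, the near-100% argument covers the decree risk class alone. Whether the decree sets other access conditions cannot be judged from this document. Patients misclassified at entry would also be found by an audit of the recorded features, so the endpoint keeps some content.

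**Conclusion.** The concern holds in a limited form. Regional differences in uptake cannot be estimated from a registry of tested patients. Compliance with the decree risk class is close to 100% by eligibility under sections 5.1 and 5.2, or depends on unit discretion if section 6 is applied. The enrolment texts contradict each other and must be reconciled.

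The range of 100%, 88.9% or 80% for a true 80% is an illustration resting on assumed p and f, not an estimate for this study. Off-criteria patients would reach the co-primary denominator only if sites use the section 6 exception, and the size of that effect cannot be derived. Both endpoints are secondary and descriptive, and the section 8.2 interval arithmetic is unaffected. The change should be made because a compliance figure produced by eligibility, or regional counts produced by site participation, could be misread as evidence on the questions section 2 calls central.

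**What to change.** 1. Reconcile the second sentence of section 6, and the matching synopsis wording, with sections 5.1 and 5.2, so that one enrolment rule applies to the retrospective and prospective cohorts. Which rule applies is for the sponsor to decide.
2. Restate the access endpoint as regional differences in test type, time from diagnosis to request and time from request to result, among tested patients at participating sites. Make no claim on regional uptake unless an external regional denominator is named.
3. Report compliance as an audit of decree class, re-derived from the recorded grade, tumour size, Ki67, nodal status and ER in enrolled patients, with a 'not derivable' category. State that it is not a prescribing compliance rate.
4. If the reconciled rule admits off-criteria patients, restrict the treatment-change analysis to decree-intermediate patients.

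The cost is a protocol amendment and narrower claims. The audit uses items that section 7.2 already lists. Widening enrolment to all tested patients would be a design choice for the sponsor and is not needed for this repair.

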8.2 Statistical analysis

It is assumed that the proportion of patients changing from chemotherapy (CT) followed by endocrine therapy (ET) to ET alone may be 50%, while the proportion of patients who change from ET to CT (followed by ET) is 10%. Therefore, the net change from CT to ET is expected to be 40%.

To demonstrate this expected impact in clinical practice, with a sample size of 1000 patients, the confidence intervals for these three estimates are expected to be 46.9%-53.1% (C.I. width of 6.2%) for changes from CT to ET; 8.3%-12.0% (C.I. width of 3.7%) for changes from ET to CT and 37.0%-43.1% (C.I. width of 6.1%) for the net change from CT to ET.

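### The changed-versus-unchanged comparison merges chemotherapy dropped with chemotherapy added, so it can partly reflect the pre-test plan and can hide opposite effects

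*Protocol*

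**What the plan says.** Section 4.2 lists, among the secondary endpoints, the distribution of characteristics "in the group of patients with changed treatment recommendation compared to the group of patients with unchanged indication after genomic test". It names two groups and does not divide them by direction of change or by pre-test indication. The examples of characteristics that it gives are "patient age, comorbidities, tumour size, number of positive lymph nodes, tumour grade".

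Other parts of the protocol bear on this:

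- **Section 4.1** gives the two directions their own lines in the co-primary endpoint. One is the saving in chemotherapy; the other is "Addition of adjuvant chemotherapy to endocrine therapy alone compared to the pre-test indication". An overall change rate stands beside them.
- **Section 8.2** assumes that 50% change from chemotherapy followed by ET to ET alone, "while the proportion of patients who change from ET to CT (followed by ET) is 10"%.
- **Section 1** words the 10% as a rate within one plan: "in about 10% of patients eligible for adjuvant endocrine therapy alone, the genomic test result will change the therapeutic approach".
- **Section 1** also says that treatment choice takes account of patient and tumour features, "including age, menopausal status, tumour size, grading and Ki67 labelling index, number of lymph nodes involved and hormone receptor expression", and that these "drive the individual adjuvant BC treatment as for recommended international guidelines".
- **Section 6** records the "pre and post-test therapeutic indication (CET vs ET), the test results" and the treatment actually received.

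**The concern.** A change of plan can mean two opposite things here, and which one is possible depends on the pre-test plan: only a CET patient can lose chemotherapy, and only an ET patient can gain it. The protocol expects change to be far more common in one direction than in the other. It also says that the characteristics to be tabulated help determine the pre-test plan.

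Two misreadings follow. A characteristic may look typical of changed patients only because it is more common among those first planned for chemotherapy. And a feature that makes dropping chemotherapy less likely but adding it more likely may show no difference at all. In either case the table describes neither the patients spared chemotherapy nor those who gained it, which is what a reader would want from it.

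**Working it through.** **Inputs.** From the protocol: change rates of 50% (CET to ET) and 10% (ET to CET), and n = 1000 (section 8.2). Not in the protocol, so assumed: the pre-test CET share s, taken as 30% to 70%, and the prevalence of a trait in each plan.

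**The protocol's own figures.** The intervals in section 8.2 (46.9%–53.1%, 8.3%–12.0%, 37.0%–43.1%) are reproduced by 95% Wilson intervals, each with denominator 1000: 46.91–53.09, 8.29–12.02 and 37.01–43.07. The denominator of 1000 matters: section 1 words the 10% as a rate within ET plans, but section 8.2 computes as if all rates were shares of the whole cohort. Both readings are worked below.

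**1. Mix of pre-test plans, rates read within plan.** The odds ratio of change, CET against ET, is (0.5/0.5)/(0.1/0.9) = 9. The changed fraction is c = 0.5s + 0.1(1 − s). The CET share is 0.5s/c among changed patients and 0.5s/(1 − c) among unchanged patients.

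| s | CET share, changed | CET share, unchanged |
|---|---|---|
| 30% | 0.15/0.22 = 68% | 0.15/0.78 = 19% |
| 50% | 0.25/0.30 = 83% | 0.25/0.70 = 36% |
| 70% | 0.35/0.38 = 92% | 0.35/0.62 = 56% |

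**2. A trait unrelated to change within either plan.** Its prevalence in each pooled group is the CET prevalence times the CET share plus the ET prevalence times the ET share.

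- 30% in CET, 20% in ET, s = 50%: 28.3% of changed against 23.6% of unchanged patients, odds ratio 1.28. If tested with 300 against 700 patients, chi-square is 2.54 and p about 0.11. At s = 30% and 70% the odds ratio is 1.31 and 1.20.
- 40% in CET, 10% in ET, s = 50%: 35.0% against 20.7%, odds ratio 2.06. At s = 30% and 70% it is 2.34 and 1.64.

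The true within-plan odds ratio is 1.0 throughout.

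**3. Opposite effects.** Take s = 50% and a trait present in 40% of both plans.

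- CET plans: change in 45% with the trait and 53.3% without, odds ratio 0.72. Overall 0.4 × 0.45 + 0.6 × 0.533 = 0.50, as the protocol assumes.
- ET plans: change in 15% with and 6.7% without, odds ratio 2.47. Overall 0.4 × 0.15 + 0.6 × 0.067 = 0.10, as the protocol assumes.
- Pooled: (0.45 + 0.15)/2 = 30% with and (0.533 + 0.067)/2 = 30% without, odds ratio 1.0.

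A second example lets the split vary. Suppose the trait is present in 25% of CET-to-ET and 55% of confirmed CET patients (−30 points), and in 40% of ET-to-CET and 10% of confirmed ET patients (+30 points). The pooled table shows 29.8% against 18.7% at s = 30%, 27.5% against 26.1% at s = 50%, and 26.2% against 35.4% at s = 70%. The within-plan contrasts are identical in all three cases, yet the pooled difference changes sign.

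**4. Rates read as shares of all 1000 patients.** The changed group is 500 CET-to-ET plus 100 ET-to-CET patients, so 500/600 = 83% have a CET plan. Among unchanged patients the CET share is (s − 0.5)/0.4: 25% at s = 60%, 50% at s = 70%. The groups balance only at s = 0.5 + 0.4 × 0.833 = 83%, and the imbalance reverses above that. The two directions are merged whatever s is.

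**The case against.** The strongest reply is that this is a one-line descriptive endpoint. It names no test, model or claim about predictors, and nothing forbids a further breakdown, which a statistical analysis plan (not available for this review) could add. The pooled groups also match the overall change rate that opens the co-primary list, so there is no contradiction with section 4.1. As plain description, 35.0% against 20.7% is a true difference between the groups named.

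The sizes can be disputed too. The split, the prevalences and the within-plan effects are assumed, and the exact cancellation was constructed. The within-plan reading of 50% and 10% is not certain. Section 1 says the need for chemotherapy is unclear in intermediate-risk patients, so the link between these characteristics and the pre-test plan may be weaker in this population.

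Most of this stands as a limit on size and weight. The calculations show what can happen, not what will, and under mild assumptions the distortion is small. It does not remove the point: the protocol itself states the contrast, so this is not a detail left open. A reader of a changed-versus-unchanged table will naturally take it as showing who changes and why, and the two groups would have the same plan mix only by coincidence.

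**Conclusion.** The concern holds. The contrast in section 4.2 pools opposite outcomes, and its groups generally differ in pre-test plan. With the rates read within plan and 30% to 70% of patients planned for CET, a trait with no within-plan association shows a pooled odds ratio of 1.20–1.31 at assumed prevalences of 30% and 20%, and 1.64–2.34 at 40% and 10%. Opposite within-plan effects can pool to nothing or take either sign. With the rates read as whole-cohort shares, the imbalance depends on the unstated pre-test split and vanishes only near 83% planned CET.

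The consequence is confined to interpretation of one secondary, descriptive table. The co-primary rates, the sample size and the data collection are unaffected. The change should be made because the better contrast costs almost nothing.

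**What to change.** Reword the endpoint in section 4.2 so that characteristics are reported within each pre-test indication: among patients planned for CET, those changed to ET against those kept on CET; among patients planned for ET, those with chemotherapy added against those kept on ET. The pooled table can remain as an addition.

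The cost is a change of wording and one extra table. Section 6 already records both indications, so no new data are needed.

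The limit to state is precision in the group with chemotherapy added. With rates read within plan it has 0.1 × 1000 × (1 − s), or about 70, 50 or 30 patients at 30%, 50% or 70% planned CET. A 30% prevalence then has a 95% margin of 1.96 × √(0.3 × 0.7/n), about 11, 13 or 16 points. With rates read as whole-cohort shares the group is 100 and the margin about 9 points. Pooling does not cure this; it only places the small group inside a larger one.
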